2.4. Loss to follow-up and other missing data

Given data-sharing constraints with UPMC, outcome data is available only for participants who delivered at UPMC hospitals. LH will report how many people downloaded the app and did not deliver at UPMC. This will allow us to estimate the percentage of participants lost due to delivering out of the system.

For included participants, there is a very little missing data for the primary measure (80/13752=0.06%). We will assume that such data is missing at random and exclude participants whose data is missing for a measure from analyses involving that measure. There is no missing data for the secondary measures. The same practice will be followed for the exploratory outcomes. No imputation will be done for any outcome measures.

Missing categorical values for baseline covariates (baseline disease information and demographics) will not be imputed, but treated as an additional category. Continuous variables missing less than 5% of the data will be imputed with the median value for that variable. Two continuous baseline covariates are missing more than 5% of data ADI_NATRANK (1330/13752=9.7%) and PREGRAVID_WEIGHT (1318/13752=9.6%). For these two variables, scatterplots and Little's test will be used to investigate if the data is missing completely at random (MCAR), missing at random (MAR), or missing not at random (MNAR) on 20% of the unblinded data. If the data appears to be MCAR or MNAR, median imputation will be used. If the data is MAR, multiple imputation will be used. If multiple imputation is needed, LH will generate data for the missing values so that EG remains blinded. For all missing data, we will conduct

sensitivity analyses, repeating analyses of primary and secondary outcomes using imputed values two standard deviations above and below the median. See Appendix A for the full list of collected baseline covariates.

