2.5. Development of outcome measurements

EG will view 20% of unblinded data to determine which potential confounders to include in the outcome models, in the addition to those identified in advance, based on previous research. Section 3.1.1 provides further details on how confounders will be selected. The unblinded data will be split evenly between the MHP and usual care cohorts in order for EG to remain blinded to the treatment and control cohorts when analyzing outcomes.

EG will also create a model of the confounders of app usage to use in dose-response models and a propensity score matching model for the groups.

To allow EG to remain blinded to the final data, while performing these analyses, LH will generate random values of adherence, drawn from the distribution for the MHP cohort, for the usual care cohort. LH will run the outcome models on the full set of data and will report the results to EG for interpretation. EG will finish data analysis before being unblinded to the labels of the MHP and usual care cohorts.

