3.1.1. Analysis of primary outcomes

The difference in gestational weeks at birth will be evaluated using a linear effects model accounting for confounders of preterm birth, as measured at baseline. We estimate that about 57 out of 12,344 deliveries are for a second pregnancy for participants included in the sample given that 0.464% of participants who downloaded the app had two deliveries in the sample. We have included these women in the sample because we cannot exclude similar women in the usual care cohort given limitations in our data. Likewise, we cannot account for random effects of multiple deliveries using a mixed effects model.

Baseline study variables will be included as confounders in the model if (a) the literature has identified the variable as a confounder of preterm birth risk and (b) they might plausibly have influenced participants' decision to download the app. If, for a variable, the evidence on condition (a) is inconclusive and condition (b) is possible, we will examine the data and include the variable if it passes a 10% change-in-estimates threshold for the outcome or for the likelihood of downloading the app. The change-in-estimate will be calculated by adding each study variable to the model from the literature individually. Only baseline variables will be evaluated as potential confounders, as they could not have been affected by use of the app.

We will report the results of two models for each outcome, one using only confounders identified in the literature and one adding confounders identified empirically (Appendix A). Including fewer confounders will reduce the likelihood that the average treatment effect applies only to an unrepresentative subset of the population. Including additional confounders will reduce the likelihood of statistical bias in estimating the average treatment effect.

The dataset contains many known confounders of preterm birth that could be included in the model including:

- Previous preterm birth (3)
- Race (3)
- Low body-mass index (3,4)
- Insurance type (5)
- Area deprivation index (6)
- Multiple gestations (3)
- Previous spontaneous abortions (7)
- Hypertension (3)
- Diabetes (3)
- Tobacco use (3)

There are also many known predictors of preterm birth that are not in the EHRs, hence not available for this study. They include educational attainment, marital status, interpregnancy interval, relatives who delivered preterm, and genetic predictors of preterm birth (3).

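### The missing-covariate rule picks multiple imputation or a median fill on a MAR/MNAR distinction its diagnostics cannot make; the likely effect on the primary estimate is modest

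*SAP*

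**What the plan says.** SAP section 2.4 singles out two continuous covariates with more than 5% missing: ADI_NATRANK (1330/13752 = 9.7%) and PREGRAVID_WEIGHT (1318/13752 = 9.6%). For these, "scatterplots and Little's test will be used to investigate if the data is missing completely at random", MAR or MNAR, using the unblinded 20% subset. The label then fixes the method: "If the data appears to be MCAR or MNAR, median imputation will be used", whereas "If the data is MAR, multiple imputation will be used". Section 2.5 adds, on that subset, "The unblinded data will be split evenly between the MHP and usual care cohorts".

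Other continuous covariates get no diagnostic: "Continuous variables missing less than 5% of the data will be imputed with the median value for that variable". The stated safeguard for all missing data is "repeating analyses of primary and secondary outcomes using imputed values two standard deviations above and below the median".

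Both variables bear on the primary analysis. Section 3.1.1 says "The dataset contains many known confounders of preterm birth that could be included in the model", and its list includes area deprivation and low body-mass index. Section 3.1.2 lists pre-pregnancy BMI for gestational weight gain (secondary outcome 7).

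**The concern.** Little's test has MCAR as its null hypothesis, and scatterplots show only observed values. Neither can show whether missingness depends on the unseen value, which is what distinguishes MNAR from MAR. Once MCAR is rejected, the SAP gives no criterion for the next step, yet that step selects the method.

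The rule also sends MNAR to a single constant, where such a fill has no justification. Even under MCAR the filled records carry no adjustment on that variable. In a comparison of people who downloaded an app with people who did not, covariate adjustment is the main protection against bias. At stake is a discretionary choice inside the primary model, and a sensitivity analysis that a reader could mistake for limits on the error.

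**Working it through.** **The plan's own yardstick.** From section 1.5: cohorts of 7147 and 5197, SD 10 days, 80% power; two-sided 5% is assumed, since sidedness is not stated.

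- Standard error = 10 × √(1/7147 + 1/5197) = 0.182 day.
- Detectable difference = 2.8016 × 0.182 = 0.51 day. This reproduces the SAP.

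**Inputs the SAP does not give (assumed).** Cohort gap in the covariate 0.2 to 0.5 SD; 1 to 2 days of gestation per SD; covariate entered linearly; MNAR logit slope 1; true app effect 0. Missing fraction p = 0.0967.

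**Can the diagnostics separate MAR from MNAR?** Little's test was simulated on 2,468 records (20% of 12,344), cohorts 50:50, 9.7% missing, 2,000 replicates per cell.

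| Correlation with an observed covariate | Rejects under MNAR | Rejects under matched MAR |
|---|---|---|
| 0 | 32% | 30% |
| 0.3 | 97% | 95% |
| 0.6 | 100% | 100% |

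Under MCAR it rejected in 4 to 5%. A rejection therefore says nothing useful about MAR versus MNAR. In a separate simulation, MNAR acting in opposite directions in the two cohorts was rejected in 54% to 90% of runs, so MNAR can also pass as MCAR.

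**What the median fill leaves under MCAR.** To first order the filled covariate shows only (1 − p) of the cohort gap while its slope is almost unchanged, so the residual bias is about p × gap × slope:

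- 0.0967 × 0.2 × 1 = 0.019 day
- 0.0967 × 0.5 × 2 = 0.097 day

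**Why both ends of the two-SD analysis err the same way under MCAR.** A constant placed 2 SD from the centre adds 4p(1 − p) to the covariate's variance whichever side it lies on. The slope shrinks by 1/(1 + 4p) = 1/1.387. The share of confounding left is about 1 − (1 − p)/(1 + 4p) = 1 − 0.9033/1.387 = 0.349, or 0.07 to 0.35 day over the assumed range, with the same sign at both ends.

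**Simulation.** At least 1.5 million records per case; bias in days. Imputation is by regression on cohort and outcome. Separate runs of the same case agree to within about 0.01 day.

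| Case | Median | +2 SD | −2 SD | Imputation |
|---|---|---|---|---|
| MCAR; 0.2 SD, 1 day | 0.021 | 0.074 | 0.071 | 0.002 |
| MCAR; 0.5 SD, 2 days | 0.103 | 0.361 | 0.363 | 0.001 |
| MNAR, no direct cohort effect; 0.2 SD, 1 day | 0.031 | 0.031 | 0.120 | 0.012 |
| MNAR, no direct cohort effect; 0.5 SD, 2 days | 0.154 | 0.160 | 0.597 | 0.055 |
| MNAR, 14% v 6.6% missing (smaller v larger cohort); 0.2 SD, 1 day | −0.034 | 0.124 | −0.027 | −0.062 |
| MNAR, 14% v 6.6% missing; 0.5 SD, 2 days | −0.003 | 0.426 | 0.220 | −0.125 |

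In the first four rows both two-SD ends lie on the same side of the truth. With missing rates that differ by cohort, the ends bracketed zero in 4 of 8 cases computed and not in the other 4.

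**MNAR in opposite directions by cohort.** Imputation alone was off by 0.17 to 0.34 day. A common shift of ±1 SD was still off by 0.14 to 0.40. Shifts of −1 and +1 SD set separately by cohort came within 0.07.

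**The case against.** Four counter-arguments carry weight.

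- **Imputation is not uniformly better.** In all four cases with MNAR missingness of 14% v 6.6%, it was more biased than the median fill, at worst about −0.125 v −0.003 day. This stands, and it limits what the remedy can claim.
- **The upper sizes need strong inputs.** A 0.5 SD gap at 2 days per SD is 1.0 day of confounding from one covariate, about twice the detectable difference, and nothing in the SAP supports it. Section 3.1.1 also concedes several wholly unmeasured predictors, beside which a tenth of one covariate's confounding is small. This stands.
- **A linear term may not suit weight.** The primary list names low BMI, and Appendix A has no variable coded that way. With a low-BMI indicator (assumed cut-off −1.5 SD, 4.5-day effect, gap 0.3 SD) the median-fill bias was 0.001 to 0.015 day. The sizes above fit area deprivation better than weight. Section 3.1.1 also says only that the listed variables could be included.
- **The discretion is limited.** The choice is made once, on the 20% subset, and constant-fill sensitivity results are reported either way. That is true, but those results use the same device and do not bound the error.

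A reader might infer from the gap between the two branches, up to 0.12 day, that the median fill does that much harm. It does not follow: that maximum is −0.003 minus −0.125, a case where the median fill is almost unbiased and imputation is the one that is off. A reader might also infer that the primary result is unreliable because of this rule. Neither the SAP's figures nor the calculations support that.

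**Conclusion.** The rule is wrongly specified and should be changed. That conclusion rests on the wording of section 2.4 and on what the named diagnostics can show, and it is held with high confidence. The sizes are conditional on assumed inputs. Under MCAR the median fill leaves about 10% of the covariate's confounding, 0.02 to 0.10 day, which is at most a little over half of the 0.18-day standard error and a fifth of the 0.51-day detectable difference. It would not overturn a clear result but could move one close to p = 0.05. The effect may be smaller still if weight enters only as a low-BMI indicator.

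The two-SD fills show that results depend on the fill, but they should not be presented as limits on the bias.

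**What to change.** **Main method.** Remove the MCAR/MAR/MNAR branch. Use multiple imputation for ADI_NATRANK and PREGRAVID_WEIGHT whatever the diagnostics show, with cohort, outcome and all model covariates in the imputation model.

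**Sensitivity.** For these two variables, replace the two-SD constants with delta-adjusted imputations over a range justified and fixed in advance, including deltas that differ by cohort. Add a complete-case fit as a comparison only: it was within 0.01 day of the truth when missingness did not depend on the outcome, but off by 0.47 day when it did so in one cohort (assumed logit slope −0.5 per SD).

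**Secondary outcome 7.** Pre-pregnancy weight helps define sufficient gestational weight gain, and section 2.4 bars imputing outcomes. Records without it should be treated as missing that outcome and excluded under the SAP's own rule. The statement in section 2.4 that the secondary measures have no missing data needs reconciling with the 9.6%.

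**Cost.** SAP wording and modest computing, including combining imputations across the weighting, matching and dose-response analyses. Section 2.4 already assigns the generation of imputed values to the unblinded analyst. The real effort is justifying the cohort-specific delta range, because imputation alone does not remove MNAR bias.

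**Separate reporting corrections, which do not bear on the rule.**

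- Section 2.4 states that "there is a very little missing data for the primary measure (80/13752=0.06"%, but 80/13752 = 0.58%.
- The denominator 13,752 exceeds the 12,344 deliveries in section 1.5 by 1,408. Reconcile the two and restate the missing rates on the analysis sample.
- The 0.051 that section 1.5 labels as days is in SD units: 0.051 × 10 = 0.51 day, as its next sentence shows.

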1.3. Method of allocation of groups

Participants seeking prenatal care at the UPMC were offered a prescription to download the MyHealthyPregnancy app during an early prenatal visit. Participants were prescribed the app by

¹ Gestational weight gain will be evaluated based on 2009 Institute of Medicine guidelines (11). Recommended gestational weight gain depends on pregravid BMI and if it is a singleton or multiple pregnancy.

their obstetrician or the EHR system and had the option of downloading the app and consenting to trial participation. We have no direct knowledge of how obstetricians decided whether to offer the prescription or if there was encouragement to download the app in addition to the automated EHR prescription. Participants who downloaded the app will be categorized as the MyHealthyPregnancy (MHP) cohort. Participants who did not download the app will be categorized as the usual care cohort.

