1.6. Overview of proposed analyses

EG will analyze the primary, secondary, and exploratory outcomes for the trial data. LH will generate data and run models as needed so that EG remains blinded to the identity of each cohort (see section 2.5).

The primary analyses will be multiple linear regression models estimating average treatment effects of the MHP app. Secondarily, dose-response models will be created for the primary and secondary outcomes in order to understand the moderating effects of app usage.

The primary and secondary outcomes for the study will come from electronic health record (EHR) data for trial participants. Given the source and the nature of care for women who deliver in the UPMC system, few outcome data are missing data. As such, imputation will not be used to account for missing outcome data. Instead, participants will be excluded from analyses, if their outcome data is missing for an outcome measure.

As a sensitivity analysis, propensity score matching will be used to create similar cohorts of participants, excluding participants whose propensity scores are outside the overlap in the covariate distributions for the covariates that predict downloading the MHP app (see section 3.1.5). We will calculate average treatment effects for these matched subsets of participants. Inverse probability of treatment weighting will be used as an additional sensitivity analysis to account for the potential lack of overlap in covariate distributions between the study cohorts.

2. Data analysis plan – data description

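### Imputing pre-pregnancy weight also imputes the weight-gain outcome (secondary outcome 7), which the plan says it will not do

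*SAP*

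**What the plan says.** SAP section 2.4 sets out two regimes. For outcomes, participants with a missing value are left out of the analysis concerned: "No imputation will be done for any outcome measures". Section 1.6 agrees: "imputation will not be used to account for missing outcome data". Section 2.4 adds: "There is no missing data for the secondary measures".

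For baseline covariates, continuous variables are imputed. Two exceed the 5% missingness limit. One is the area deprivation rank; the other is reported as "PREGRAVID_WEIGHT (1318/13752=9.6" per cent. These two get median imputation if the data look MCAR or MNAR, and multiple imputation if they look MAR. The last rule of the covariate paragraph, whose scope is given only by the opening "For all missing data, we will conduct", announces further runs, described as "sensitivity analyses, repeating analyses of primary and secondary outcomes using imputed values two standard deviations above and below the median".

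Secondary objective 7 (section 1.1.2) is sufficient gestational weight gain. Its footnote says: "Recommended gestational weight gain depends on pregravid BMI and if it is a singleton or multiple pregnancy". Appendix A types PREGRAVID_WEIGHT as a baseline covariate and MOM_DELIVERY_WT as a secondary outcome. Section 3.1.2 lists pre-pregnancy BMI as a confounder in the outcome 7 model.

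**The concern.** Pre-pregnancy weight has two roles and section 2.4 recognises only one. As an adjuster it may be imputed. As the starting point of weight gain it is part of an outcome, and outcomes are not to be imputed. A programmer following section 2.4 would fill in the weight and then compute a gain, a BMI class and a sufficiency status from the filled-in value, with nothing telling them to stop.

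At stake is the result for one of nine secondary outcomes. For about a tenth of deliveries, the recorded status would depend heavily on an imputation constant. The ±2 SD runs, meant to show robustness, would for this outcome mostly show what the constant does.

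**Working it through.** **1. The plan's own figures.** 1318/13,752 = 9.58% and 1330/13,752 = 9.67%, so the stated 9.6% and 9.7% reproduce. Section 1.5 gives a final sample of 12,344 deliveries, and the SAP does not say how many of the 1318 are among them (if all, 1318/12,344 = 10.7%). I carry 9.6% forward.

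**2. Is pre-pregnancy weight part of outcome 7?** The SAP never writes the formula. Gain needs a start and an end weight. Appendix A lists one of each: PREGRAVID_WEIGHT and MOM_DELIVERY_WT. Pregravid BMI, which selects the recommended gain, needs the same start weight with MOM_HEIGHT. The obesity flags at first visit give neither a start weight nor the non-obese BMI classes. So a delivery without pre-pregnancy weight has no observed outcome 7.

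**3. Shift between the two ±2 SD runs.** Let D be delivery weight, M the median and s the SD of pre-pregnancy weight.

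- Run at +2 SD: gain = D − (M + 2s)
- Run at −2 SD: gain = D − (M − 2s)
- Difference = 4s for every affected delivery

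The SAP does not give s. Assuming 15 to 20 kg, 4s = 60 to 80 kg; assuming 12 to 22 kg, 4s = 48 to 88 kg.

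**4. What the affected deliveries would look like.** A simulation, all inputs assumed: pre-pregnancy weight with median 72 kg and SD 12 to 22 kg; mean gain 12 to 14 kg (SD 6 to 7 kg); height 163 cm (SD 7 cm); BMI-dependent minimum gains of 5 to 12.5 kg and maxima of 9 to 18 kg.

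| Start weight used | Median computed gain (kg) | Negative gain | At or above minimum | Within band |
|---|---|---|---|---|
| True value | 12 to 14 | 2% | 72–79% | 20–25% |
| Median | 12 to 14 | 14–27% | 59–69% | 8–13% |
| Median + 2 SD | −10 to −32 | 75–89% | 8–15% | 2–5% |
| Median − 2 SD | 36 to 58 | about 0% | 98–100% | 1–4% |

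The second row matters most: plain median imputation, a planned main method, already distorts the outcome.

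**5. Effect on the cohort contrast.** Let m1 and m2 be the missing fractions, p1 and p2 the rates in observed deliveries, and c (0 or 1) the status forced on the rest. The rate in cohort k is (1 − mk)pk + mk·c.

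- Equal missingness, m1 = m2 = 0.0958: contrast = 0.904(p1 − p2). A 5-point difference becomes 4.5.
- Unequal missingness, p1 = p2 = p: contrast = (m1 − m2)(c − p). With p = 0.5, a 2 to 4 point gap in missingness creates a spurious 1 to 2 points in each run, with opposite signs if c flips, so 2 to 4 points between runs.

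For scale, the difference detectable with 80% power at an assumed 50% rate is 2.80 × √[0.25(1/7147 + 1/5197)] = 2.6 points.

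**The case against.** **Scope of the ±2 SD sentence.** A reader might infer from "For all missing data, we will conduct" that the missing gestational ages are also to be imputed, a flat contradiction on the primary outcome. The text does not firmly support that. The sentence closes the covariate paragraph, is followed by a pointer to the list of baseline covariates, and can be read as repeating outcome analyses with imputed covariates. It is a scope ambiguity. Its effect would also be small: 80 values moved by 2 × 10 = 20 days shift the contrast by about 0 if missingness is proportional, by 20 × 80/7227 = 0.22 day if all fall in the larger cohort, and by 20 × 80/5277 = 0.30 day if all fall in the smaller, against a detectable 0.51 day. The weight-gain problem survives the narrow reading, because pre-pregnancy weight is in that covariate list.

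**An existing rule could cover it.** If gain cannot be computed, the missing-measure rule would exclude the delivery. That is a sensible outcome, but the plan does not reach it: having stated "There is no missing data for the secondary measures", it leaves nothing to exclude.

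**The contrast need not swing.** This stands. One constant in both cohorts mainly dilutes, as step 5 shows. A large artificial change in the estimated effect cannot be inferred, because the SAP gives no missingness by cohort.

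**Flipping from sufficient to insufficient.** This presumes that sufficient means reaching a minimum. The SAP does not say. If it means lying within a range, most affected deliveries fail in both runs, though the constant still sets their status.

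**Value of the ±2 SD runs elsewhere.** For true adjusters they are a crude stress test, not a worthless one.

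**Conclusion.** The point holds for secondary outcome 7. Section 2.4 as written imputes a component of an outcome in about 9.6% of records, against its own rule, and its completeness statement cannot be right for that outcome. This applies to the planned median or multiple imputation as well as to the ±2 SD runs.

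The 4 SD shift is an identity once gain is delivery weight minus pre-pregnancy weight. That formula is an inference, though a firm one, since no other start weight is listed. The kilogram figures and the table rest on assumed distributions. The effect on the cohort comparison is mainly dilution under equal missingness, and bias of unknown size otherwise.

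The primary comparison is not undermined: there the variable can enter only as an adjuster, through BMI.

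**What to change.** 1. Define outcome 7: the gain formula, the weights used, and whether sufficient means at least a minimum or within a range.
2. Exclude deliveries without an observed pre-pregnancy weight from outcome 7 under the existing missing-measure rule, in the main and sensitivity analyses alike.
3. Replace the completeness statement with the true count of missing values for outcome 7. In the same paragraph, "very little missing data for the primary measure (80/13752=0.06" per cent should read 0.58 per cent (80/13,752).
4. State that the ±2 SD runs apply only to missing continuous baseline covariates used as adjusters (categorical ones have a missing category and no median or SD), with values kept within the possible range. For the 0–100 deprivation rank, both values stay on scale only if 4 SD ≤ 100. A uniform rank (assumed; SD 28.9) would give about −8 and 108.

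Cost: SAP wording, and about 9.6% fewer deliveries for one outcome. The detectable difference rises by a factor of 1/√0.904 = 1.05, from about 2.6 to 2.7 points at an assumed 50% rate. The complete-case analysis rests on the missing-at-random assumption that section 2.4 already makes for missing outcomes. Multiple imputation with cohort-specific shifts is an optional addition, provided the no-outcome-imputation rule is amended to allow it.
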